9.7. Other Evaluations

MINI

The MINI is a short structured diagnostic interview for DSM-5. It has an administration time of approximately 15 minutes to provide accurate structured psychiatric interview for multicenter clinical trials. Subjects will undergo MINI (a brief, structured diagnostic interview) to confirm the diagnosis of MDD and to determine if there are other psychiatric conditions present.

MGH-ATRQ

The MGH-ATRQ is used to determine treatment resistance in MDD.²¹ Information regarding all antidepressant therapies used in the current depressive episode will be recorded on the ATRQ.

The MGH-ATRQ evaluates the adequacy of duration and dosage of all antidepressant medications used for the current major depressive episode. In addition, the MGH-ATRQ assesses the degree of improvement on a scale from 0% (not improved at all) to 100% (completely improved). The MGH-ATRQ will be completed by the clinician, in collaboration with the subject.

SAFER Criteria Interview

Remote, independent psychiatrists/psychologists will perform the SAFER Interview⁶⁶ for all subjects to assess the validity of a diagnosis of depression and eligibility for the study.

SAFER refers to:

S	State versus trait	The identified symptoms must reflect the current state of illness and not longstanding traits. Traits do not generally change in 4–12 weeks.
A	Assessability	The patient's symptoms are measurable with standard, reliable rating instruments. The symptoms of valid subjects can be reliably assessed with standardized measurement tools
F	Face validity	The patient's presentation is consistent with our knowledge of the illness (symptoms map to the nosological entity; clear change from previous level of function; similar to previous episodes if recurrent)
E	Ecological validity	The patient's symptoms reflect the characteristics of the illness in a real-world setting (frequency, intensity, duration, course, impact over at least 4 weeks)
R	Rule of the 3 P's	Identified symptoms must be pervasive, persistent, and pathologic and interfere with function and quality of life

9.8. Sample Collection and Handling

The actual dates and times of sample collection must be recorded in the eCRF or laboratory requisition form. If blood samples are collected via an indwelling cannula, an appropriate amount (1 mL) of serosanguineous fluid slightly greater than the dead space volume of the lock will be removed from the cannula and discarded before each blood sample is taken. After blood sample collection, the cannula will be flushed with 0.9% sodium chloride, United States Pharmacopeia (USP) (or equivalent) and charged with a volume equal to the dead space volume of the lock.

Refer to the [TIME AND EVENTS SCHEDULE 1](#), [TIME AND EVENTS SCHEDULE 2](#), and [TIME AND EVENTS SCHEDULE 3](#) for the timing and frequency of all sample collections.

Instructions for the collection, handling, storage, and shipment of samples are found in the laboratory manual that will be provided. Collection, handling, storage, and shipment of samples must be under the specified, and where applicable, controlled temperature conditions as indicated in the laboratory manual.

10. SUBJECT COMPLETION/DISCONTINUATION OF STUDY TREATMENT/ WITHDRAWAL FROM THE STUDY

10.1. Completion

A subject will be considered to have completed the study:

- If he or she do not respond at the end of 4-week double-blind induction phase;
- If he or she relapse during posttreatment phase and complete the OL phase;
- If he or she complete 24-week posttreatment phase without relapse.

Subjects who prematurely discontinue study treatment for any reason before completion of the double-blind induction phase will not be considered to have completed the double-blind induction phase of the study. In addition, subjects who prematurely discontinue study treatment

for any reason before completion of the posttreatment or OL phases, will not be considered to have completed the posttreatment phase of the study.

10.2. Withdrawal From the Study

Withdrawal From the Study

A subject will be withdrawn from the study for any of the following reasons:

- Lost to follow-up
- Withdrawal of consent (Note: See “Withdraw of Consent” section below; this should only be selected as a reason for withdrawal if the subject does not agree to any further study assessments or procedures. If the subject is agreeable to participating in the EW visit and the follow-up phase, another reason for withdrawal should be selected.)
- Violation of protocol procedures (determined on a case-by-case basis)
- Blind is broken (double-blind induction phase)
- Lack of efficacy
- The investigator or sponsor believes (eg, that for safety or tolerability reasons such as an AE) it is in the best interest of the subject to discontinue the study. See also guidance on blood pressure monitoring on intranasal dosing days (Section 6.3.1).
- At any time point after baseline (Day 1, predose), the subject has a:
 - QTcF change from baseline ≥ 60 msec and QTcF > 480 msec, or
 - QTcF > 500 msec.
- Noncompliance to switched oral antidepressant therapy (missing > 2 days per consecutive 7 days)
- Subject becomes pregnant
- Study is terminated by sponsor for futility
- Death

If the subject withdraws from the study before the end of the double-blind induction phase, an EW visit is to be performed.

If a subject is lost to follow-up, every reasonable effort must be made by the study-site personnel to contact the subject and determine the reason for discontinuation/withdrawal. This should include at least 3 telephone calls, certified letters, email requests, etc. To ensure access to follow-up subjects, the study-sites should attempt to obtain both primary and secondary telephone contact numbers (eg, home, work, and mobile phone numbers), as well as other contact information (eg, email addresses) from subjects before randomization. In addition, the study-site should emphasize the importance of follow-up information to the subject before randomization. The measures taken to follow up must be documented.

When a subject withdraws before completing the study, the reason for withdrawal is to be documented in the eCRF and in the source document. Subjects who withdraw will not be replaced.

Withdrawal of Consent

Every effort will be made in the study to ensure withdrawal of consent is not selected as a reason for discontinuation when in fact the subject withdrew for an identifiable reason (eg, due to an AE or lack of efficacy).

Subjects who wish to withdraw from the study should be asked if they are agreeable to be contacted to collect follow-up information. Subjects who are not agreeable to follow-up contact will be withdrawn from the study as “withdrawal of consent.” Subjects who no longer wish to take study drug but agree to provide follow-up information will be withdrawn from the double-blind induction phase with the reason noted as “Other” and will specify the reason why.

For a subject who “withdraws consent”, it is recommended that the subject withdraw consent in writing; if the subject refuses or is physically unavailable, the study-site should document and sign the reason for the subject’s failure to withdraw consent in writing and maintain it with the subjects source records.

The investigator will be responsible for making all required notifications to the Institutional Review Board (IRB).

10.3. Withdrawal From the Use of Research Samples

Withdrawal From the Use of Samples in Future Research

The subject may withdraw consent for use of samples for research (refer to Section 16.2.5, Long-Term Retention of Samples for Additional Future Research). In such a case, samples will be destroyed after they are no longer needed for the clinical study. Details of the sample retention for research are presented in the ICF.

11. STATISTICAL METHODS

Statistical analysis will be done by the sponsor or under the authority of the sponsor. A general description of the statistical methods to be used to analyze the efficacy and safety data is outlined below. Specific details will be provided in the Statistical Analysis Plan (SAP).

11.1. Subject Information

The primary efficacy (FAS) and safety analysis sets are defined below.

- **Full Analysis Set:** All randomized subjects who receive at least 1 dose of intranasal study drug in the double-blind induction phase.
- **Open-label Analysis Set:** All subjects who receive at least 1 dose of intranasal study drug in the OL induction phase.

- **Safety Analysis Set:** All randomized subjects who receive at least 1 dose of intranasal study drug in the double-blind induction phase.

11.2. Sample Size Determination

The sample size for this study was calculated assuming a treatment difference for the double-blind induction phase of 4, 4.5, 5 points in MADRS total score between each dose (28 mg, 56 mg, 84 mg) of esketamine and the placebo respectively, a SD of 10 for each treatment group, a 1-sided significance level of 0.05 and a drop-out rate of 12.5%. A total of 183 subjects will need to be randomized to treatment in a 2:1:1:1 ratio (72 subjects on placebo group and 37 subjects per intranasal esketamine dose group) to achieve 80% power to detect difference for at least one dose group of intranasal esketamine to placebo using a Dunnett adjustment. The treatment difference and SD used in this calculation were assumed based on results of Panel B of the ESKETINTRD2003 study with clinical consideration.¹⁶

11.3. Interim Analysis

No interim analysis is planned. The first database lock will occur after that all subjects will complete the double-blind induction phase.

11.4. Efficacy Analyses

Efficacy analysis will be performed on the FAS, which will include all randomized subjects who receive at least 1 dose of intranasal study drug in the double-blind induction phase. Unless otherwise specified, a 1-sided significance level of 0.05 will be used. For the primary efficacy analysis, change from baseline in MADRS total score at Week 4 in the double-blind induction phase will be analyzed using a MMRM. The model will include baseline MADRS total score as a covariate, and treatment, day, and day-by-treatment interaction as fixed effects. An unstructured variance-covariance matrix will be used. Comparison of each esketamine dose groups with the placebo group will be performed with the appropriate contrast using a Dunnett adjustment.

The impact of the missing data on the efficacy results will be assessed using sensitivity analyses. The follow-up data from subjects who discontinued the double-blind induction phase will be incorporated in the sensitivity analyses. Methods of sensitivity analyses will be specified in the SAP.

For the secondary efficacy analysis, the dose-response relationship will be investigated using the MCP-Mod procedure. Details will be provided in the SAP.

The other secondary efficacy endpoints, the endpoints with continuous values will be analyzed by using MMRM similar to the primary endpoint. Comparison of each esketamine group versus placebo group will be performed using the appropriate contrast. Binary endpoints will be analyzed using Fisher's exact test with 90% CIs for the proportion provided for each treatment group.

Time to relapse will be defined as the time between the end of the double-blind induction phase and the first documentation of a relapse event during the posttreatment phase. This will be analyzed separately either remitters or responders (but who are not remitters) at the end of the double-blind induction phase. Summary statistics (eg, number of relapses, number of censored subjects, median 25th and 75th percentile) will be provided from the Kaplan-Meier method.

Additionally, scores and the changes from baseline of all efficacy endpoints will be summarized for all visits in the each induction phase. Data from the OL induction phase will be summarized based on subjects who received treatment during the OL induction phase.

11.5. Pharmacokinetic Analyses

Plasma esketamine (and noresketamine and other metabolites, if needed) concentrations will be listed for all subjects. Descriptive statistics of plasma esketamine (and noresketamine or other metabolites, if needed) concentration at each PK assessment time points will be calculated by dose.

All concentrations below the lowest quantifiable sample concentration of the assay (BQL) or missing data will be labeled as such in the concentration data listing. All subjects and samples excluded from the analysis will be clearly documented in the study report.

Population PK analysis of plasma concentration-time data of esketamine (and noresketamine or other metabolites, if needed) will be performed with non-linear mixed-effects modeling (NONMEM) approach. If deemed necessary, data will be combined with data from other studies. Details will be given in a population PK analysis plan and the results of the population PK analyses will be presented in a separate report.

11.6. Biomarker and Pharmacogenomic Analyses

Baseline biomarker values and changes from baseline to the time points specified in the [TIME AND EVENTS SCHEDULE 1](#) will be assessed. Biomarker values will be tabulated by treatment group over time points and summary statistics will be calculated. Associations between biomarkers and clinical endpoints will be explored. Correlations between baseline values and change in baseline values with efficacy and other clinical evaluations will be assessed, including the relation with response, maintenance of response, illness relapse, and nonresponse.

Pharmacogenomic analyses may include candidate gene analyses or genome-wide association analyses in relation to treatment response, maintenance/stabilization of response, relapse, and nonresponse.

Details of the analysis plan and summary of results from both biomarker and pharmacogenomics analyses will be provided in a separate report.

11.7. Pharmacokinetic/Pharmacodynamic Analyses

The PK/PD relationship of intranasal esketamine and MADRS total score (and possibly selected AEs as additional PD parameters may be evaluated. If there is any visual trend in graphical analysis, suitable models will be applied to describe the PK/PD relationships. The results of the PK/PD evaluation will be presented in a separate report.

11.8. Safety Analyses

Safety analysis set will consist of all randomized subjects who receive at least 1 dose of intranasal study drug in the double-blind induction phase. Safety data for the double-blind period will be analyzed for this population. For the analysis of safety data in the OL induction phase, all subjects who received at least 1 dose of intranasal study drug in this period will be analyzed.

Adverse Events

For each AE, the number of subjects who experience at least 1 occurrence of the given event will be summarized by treatment group.

The verbatim terms used in the eCRF by investigators to identify AEs will be coded using the Medical Dictionary for Regulatory Activities (MedDRA). The TEAEs are AEs with onset during the treatment phase or that are a consequence of a preexisting condition that has worsened since baseline. All reported AEs will be included in the analysis. For each AE, the percentage of subjects who experience at least 1 occurrence of the given event will be summarized by treatment group. In addition, comparisons between treatment groups will be provided if appropriate.

The TEAEs of special interest will be examined separately (please refer to Section 3.2.6). The AEs of special interest will be further listed in the SAP.

Summaries, listings, datasets, or subject narratives may be provided, as appropriate, for those subjects who die, who discontinue treatment due to an AE, or who experience a severe or an SAE.

Clinical Laboratory Tests

Laboratory data will be summarized by type of laboratory test. Markedly abnormal results (specified in the SAP) will be used in the summary of laboratory data. Descriptive statistics will be calculated for each laboratory analyte at each respective scheduled time point in each phase of the study. Changes from baseline results will be presented. Frequency tabulations of the abnormalities will be made. A listing of subjects with any markedly abnormal laboratory results will also be provided.

Electrocardiogram (ECG)

The effects on cardiovascular variables will be evaluated by means of descriptive statistics and frequency tabulations. These tables will include observed values and changes from baseline values.

Electrocardiogram data will be summarized by ECG parameter. Descriptive statistics will be calculated at baseline and for observed values and changes from baseline at each scheduled time point. Frequency tabulations of the abnormalities will be made.

The ECG variables that will be analyzed are heart rate, PR interval, QRS interval, QT interval, and corrected QT (QTc) interval using the following correction methods: QT corrected according to Bazett's formula (QTcB) and QTcF.^{2,31,60}

Descriptive statistics of QTc intervals and changes from baseline will be summarized at each scheduled time point. The percentage of subjects with QTc interval >450 milliseconds, >480 milliseconds, or >500 milliseconds will be summarized, as will the percentage of subjects with QTc interval increases from baseline >30 milliseconds or >60 milliseconds.

All clinically relevant abnormalities in ECG waveform that are changes from the baseline readings will be reported (eg, changes in T-wave morphology or the occurrence of U-waves).

Vital Signs

Descriptive statistics of temperature, heart rate, pulse oximetry, respiratory rate, and blood pressure (systolic and diastolic) (supine) values and changes from baseline will be summarized at each scheduled time point. The percentage of subjects with values beyond clinically important limits will be summarized.

Physical Examination

Results of physical examinations (abnormalities) will be listed.

C-SSRS

Suicide-related thoughts and behaviors based on the C-SSRS will be summarized by treatment group in incidence and shift tables. Separate endpoints for suicidal ideation and suicidal behavior will be defined and summarized descriptively by treatment group. Missing scores will not be imputed.

PWC-20, CADSS, CGADR, MOAA/S, BPRS+, and POMS-2

Physician Withdrawal Checklist; 20-item (PWC-20) rating scale, dissociative data from the CADSS, alertness data from the CGADR, sedation data from the MOAA/S, psychosislike effect data from the BPRS+ and abuse-liability data from POMS-2 will be summarized descriptively at each scheduled visit by treatment group.

12. ADVERSE EVENT REPORTING

Timely, accurate, and complete reporting and analysis of safety information from clinical studies are crucial for the protection of subjects, investigators, and the sponsor, and are mandated by regulatory agencies worldwide. The sponsor has established Standard Operating Procedures in conformity with regulatory requirements worldwide to ensure appropriate reporting of safety information; all clinical studies conducted by the sponsor or its affiliates will be conducted in accordance with those procedures.

12.1. Definitions

12.1.1. Adverse Event Definitions and Classifications

Adverse Event

An AE is any untoward medical occurrence in a clinical study subject administered a medicinal (investigational or non-investigational) product. An AE does not necessarily have a causal relationship with the treatment. An AE can therefore be any unfavorable and unintended sign (including an abnormal finding), symptom, or disease temporally associated with the use of a medicinal (investigational or non-investigational) product, whether or not related to that medicinal (investigational or non-investigational) product. (Definition per International Conference on Harmonization [ICH])

This includes any occurrence that is new in onset or aggravated in severity or frequency from the baseline condition, or abnormal results of diagnostic procedures, including laboratory test abnormalities.

Note: The sponsor collects AEs starting with the signing of the ICF (refer to Section 12.3.1, All AEs, for time of last AE recording). Exacerbation of primary disease is not defined as AE.

Serious Adverse Event

An SAE based on ICH and EU Guidelines on Pharmacovigilance for Medicinal Products for Human Use is any untoward medical occurrence that at any dose:

- Results in death
- Is life-threatening
(The subject was at risk of death at the time of the event. It does not refer to an event that hypothetically might have caused death if it were more severe.)
- Requires inpatient hospitalization or prolongation of existing hospitalization
- Results in persistent or significant disability/incapacity
- Is a congenital anomaly/birth defect
- Is a suspected transmission of any infectious agent via a medicinal product
- Is Medically Important*

*Medical and scientific judgment should be exercised in deciding whether expedited reporting is also appropriate in other situations, such as important medical events that may not be immediately life-threatening or result in death or hospitalization but may jeopardize the subject or may require intervention to prevent 1 of the other outcomes listed in the definition above. These should usually be considered serious.

If a serious and unexpected AE occurs for which there is evidence suggesting a causal relationship between the study drug and the event (eg, death from anaphylaxis), the event must

be reported as a serious and unexpected suspected adverse reaction even if it is a component of the study endpoint (eg, all-cause mortality).

Unlisted (Unexpected) Adverse Event/Reference Safety Information

An AE is considered unlisted if the nature or severity is not consistent with the applicable product reference safety information. For esketamine, the expectedness of an AE will be determined by whether or not it is listed in the Investigator's Brochure.

Adverse Event Associated With the Use of the Drug

An AE is considered associated with the use of the drug if the attribution is possible, probable, or very likely by the definitions listed in Section 12.1.2, Attribution Definitions.

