9.2.1.2.3. Time to Relapse

Relapse is defined as any of the following:

- MADRS total score ≥ 22 for 2 consecutive assessments. The date of the second MADRS assessment will be used for the date of relapse.
- Hospitalization for worsening depression or any other clinically relevant event determined per clinical judgment to be suggestive of a relapse of depressive illness such as suicide attempt, completed suicide, or hospitalization for suicide prevention. If hospitalized for any of these events, the start date of hospitalization will be used for the date of relapse. Otherwise the date of the event will be used if the subject is not hospitalized.
- In case both relapse criteria are met, the earlier date will be defined as the date of relapse for this subject.

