12.3.2. Serious Adverse Events

All SAEs occurring during the study must be reported to the appropriate sponsor contact person by study-site personnel within 24 hours of their knowledge of the event.

Information regarding SAEs will be transmitted to the sponsor using the SAE Form, which must be completed and signed by a physician from the study-site, and transmitted to the sponsor within 24 hours. The initial and follow-up reports of an SAE should be made by facsimile (fax).

All SAEs that have not resolved by the end of the study, or that have not resolved upon discontinuation of the subject's participation in the study, must be followed until any of the following occurs:

- The event resolves
- The event stabilizes
- The event returns to baseline, if a baseline value/status is available
- The event can be attributed to agents other than the study drug or to factors unrelated to study conduct
- It becomes unlikely that any additional information can be obtained (subject or health care practitioner refusal to provide additional information, lost to follow-up after demonstration of due diligence with follow-up efforts)

Suspected transmission of an infectious agent by a medicinal product will be reported as an SAE. Any event requiring hospitalization (or prolongation of hospitalization) that occurs during the

course of a subject's participation in a study must be reported as an SAE, except hospitalizations for the following:

- Hospitalizations not intended to treat an acute illness or AE (eg, social reasons such as pending placement in long-term care facility).
- Surgery or procedure planned before entry into the study (must be documented in the eCRF). Note: Hospitalizations that were planned before the signing of the ICF, and where the underlying condition for which the hospitalization was planned has not worsened, will not be considered SAEs. Any AE that results in a prolongation of the originally planned hospitalization is to be reported as a new SAE.

The cause of death of a subject in a study, whether or not the event is expected or associated with the study drug, is considered an SAE.

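### The exemption of primary-disease exacerbation from AE reporting in Protocol 12.1.1 has no limits, conflicts with the Protocol's own SAE and recording rules, and leaves worsening or rebound depression open to inconsistent reporting

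*Protocol*

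**What the plan says.** Protocol 12.1.1 first gives a broad AE definition: "This includes any occurrence that is new in onset or aggravated in severity or frequency from the baseline condition". The note that follows then states "Exacerbation of primary disease is not defined as AE". It sets no limit by seriousness, cause or phase.

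The SAE definition in the same section lists "Requires inpatient hospitalization or prolongation of existing hospitalization" as a criterion. Section 12.3.2 adds the operating rule: "Any event requiring hospitalization (or prolongation of hospitalization) that occurs during the" subject's participation "must be reported as an SAE, except hospitalizations for the following". The exceptions are admissions of the kind described as "Hospitalizations not intended to treat an acute illness or AE (eg, social reasons such as pending placement in long-term care facility", and surgery, procedures or hospitalizations planned in advance. Section 12.3.1 requires every event that meets the SAE definition to be reported as one, even if it is also a protocol-specified assessment.

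Three other places bear on recording and counting:
- Section 8 requires a new or worsening condition treated with a concomitant medication to be entered in the AE section of the eCRF.
- Section 9.6 requires clinically relevant changes during the study to be entered there.
- Section 11.8 includes among TEAEs those that are "a consequence of a preexisting condition that has worsened since baseline". SAP 5.1 defines a TEAE by new onset or increased severity. Neither mentions the exemption.

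**The concern.** Worsening depression is the most foreseeable clinical event in this population, and the Protocol gives sites more than one answer on how to report it. An investigator whose subject is admitted for worsening depression can read one section and conclude that there is no AE, then read another and conclude that an SAE report is due within 24 hours. For worsening without admission, the note says not to report, while the general definition and Sections 8 and 9.6 say to record.

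Two things are at stake. The AE and SAE tables could reflect which section a site happened to follow as well as what happened to subjects. Rebound is also affected: withdrawal or rebound symptoms after stopping intranasal drug are a secondary safety objective (Protocol 2.1), yet rebound depression looks the same as exacerbation of the primary disease. A site that applies the note would not enter the event, and the SAP's special-interest category could not then pick it up.

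**Working it through.** The documents give no figure to reproduce, so the check is to take each type of event through the rules.

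**1. Worsening of depression that leads to admission.**
- Note in 12.1.1: not an AE.
- General definition in 12.1.1: an AE, because it is aggravated from baseline.
- SAE criterion and 12.3.2: a mandatory SAE. Admission for worsening depression is neither a social or non-acute admission nor a planned one, so no listed exception applies.
- 12.3.1: must be reported.
- Result: a direct contradiction, with no precedence rule.

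**2. Worsening that meets no seriousness criterion.**
- Note in 12.1.1: not an AE.
- General definition in 12.1.1: an AE.
- Section 8: on the AE page if treated with a concomitant medication. Section 9.6: on the AE page if clinically relevant.
- Sections 12.3.1 and 12.3.2: do not force reporting, because no SAE criterion is met.
- Result: a genuine ambiguity. If the note is followed, the event is absent from the AE tables.

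**3. Rebound depression after the last intranasal dose, non-serious.**
- Same rules as case 2.
- SAP 5.1 lists *Rebound effect* and withdrawal terms among AEs of special interest, so the analysis expects such events in the AE data.
- Result: the analysis plan expects what the reporting rule may remove.

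**4. Suicide attempt, admission for suicide prevention, or death.**
- 12.3.2: an admission is an SAE, and so is the cause of any death.
- Section 9.2.1.2.3 counts events "such as suicide attempt, completed suicide, or hospitalization for suicide prevention" as relapse, but this is an efficacy definition and contains no reporting exemption.
- C-SSRS is collected and tabulated separately.
- Result: reportable on a plain reading. A loss of events is not shown.

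**Section 11.8.** It describes TEAEs as a kind of AE. An event already excluded from being an AE does not become a TEAE through 11.8. The conflict there is indirect: the section speaks of worsened preexisting conditions without saying that the primary disease is excepted.

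**Do other data fill the gap?** Only in part. MADRS, CGI-S, C-SSRS and PWC-20 record symptoms, but they do not replace an AE report with its causality judgment or the 24-hour SAE duty. Relapse is defined only in the posttreatment phase, which only responders enter, so it does not capture an admission during double-blind induction or nonresponder follow-up. In the posttreatment phase, C-SSRS and AE review are scheduled at clinic visits. From Day 81 these fall on Days 109, 137, 165 and 193, that is, every 28 days (109 − 81 = 28), and the weekly contacts between are remote MADRS interviews only.

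**The case against.** The strongest reply is that the note limits what counts as an AE, while serious events are caught by other rules. The SAE definition rests on untoward medical occurrences in general and not on the AE definition. Section 12.3.1 requires all SAE-qualifying events to be reported, and 12.3.2 is mandatory for admissions. Amendment 1 added the sentence deliberately, to clarify the handling of primary-disease exacerbation, and keeping ordinary fluctuation of the efficacy outcome out of AE tables is a reasonable convention. Withdrawal symptoms have their own instrument, the PWC-20, which SAP 5.5.6 compares with the end of induction. Withdrawal for lack of efficacy is a separate reason in Protocol 10.2, and SAP 3.2 tabulates discontinuation reasons by group.

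Most of this stands, and it rules out several stronger readings that a reader might infer:
- *That suicidality-related admissions or deaths will be undercounted.* They fall under 12.3.2, and C-SSRS adds separate capture. The completed suicide reported in the follow-up phase of the earlier study's Japanese panel does not change this, because a death here would be an SAE.
- *That 11.8 turns exempted events into TEAEs.* It starts from AEs, so it cannot.
- *That rebound is removed from AE reporting altogether.* The SAP lists rebound and withdrawal terms, and PWC-20 is planned. The risk is confined to rebound that a site reads as disease exacerbation.
- *That the treatment comparison is biased.* Subjects stopped for worsening may be recorded under lack of efficacy and so be absent from the table of TEAEs leading to discontinuation, but they stay visible in the disposition tables. The rule is the same in all blinded arms, and no direction of bias can be shown.

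The reply does not supply a precedence rule. The note does not refer to 12.3.1 or 12.3.2 and does not say that it covers only non-serious events. The clause in 12.1.1 that keeps endpoint components reportable itself begins from a serious and unexpected AE, so a site that has applied the note may stop before reaching it. Nothing in the reply resolves the conflict with Sections 8 and 9.6.

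**Conclusion.** The exemption in 12.1.1 is wrong as written because it is unbounded. It contradicts 12.3.1 and 12.3.2 for hospitalized or otherwise serious worsening of depression. For non-serious worsening it conflicts with the general AE definition in its own section and with Sections 8 and 9.6. The supportable consequence is that serious worsening may be reported inconsistently across sites, and that non-serious worsening or rebound depression may be missing from the AE tables.

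The size cannot be derived. The documents give no expected rate of exacerbation, rebound or psychiatric admission, and the number of randomized subjects (183) does not provide one. The conclusion rests on one assumption: that sites have no instruction outside the Protocol and SAP that settles which rule prevails.

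**What to change.** Bound the sentence in Protocol 12.1.1, for example: worsening of depressive symptoms that is captured by the efficacy scales and meets no seriousness criterion need not be reported as an AE; any exacerbation that meets a seriousness criterion is reported as an SAE, whether or not it also counts as relapse; an event that the investigator judges to be a withdrawal or rebound effect is reported as an AE.

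Then reconcile Sections 8, 9.6, 11.8 and 12.3.2 with that wording. Amend SAP 5.1 to repeat the exemption in the TEAE definition and to say how events that are both an SAE and a relapse are tabulated. Further reporting triggers, such as worsening that leads to stopping of study drug, are a matter of sponsor preference and are not needed to remove the contradiction.

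The cost is a one-paragraph clarification, matching edits and a memo to sites. Visits, treatment and efficacy analyses do not change. The downside is somewhat more AE and SAE reports, some of them overlapping with relapse events.
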